If patients fail the SBT, they will be placed on the previous PEEP (prior to oxygenation test) and PS equal to the delta P (PIP-PEEP) on the previous ventilator support. The protocol will then make recommendations every 2 hours regarding weaning based on whether PRP has been in a range to wean, or a range to go back up on support (Figure 2). Clinicians will ultimately decide whether or not to accept these recommendations, and again reasons for rejection will be tracked. Once the patient achieves PS level of ≤ 8 cmH₂O, another SBT on CPAP will be recommended. If it has been 24 hours since the last SBT, regardless of PRP, another SBT will also be recommended. The clinician will chose whether or not to accept or reject the recommendation, and again reasons for rejection will be tracked. If the patient passes the SBT, the recommendation will be for extubation. If the patient fails the SBT, PS will be returned to its

previous level. No SBT recommendation will be made between 10pm-6am, so that extubation will take place at accepted times for extubation in our ICUs.

The PRP targets for weaning versus increasing support are based on analysis of the existing data from patients on PS and CPAP just prior to extubation, who were enrolled in the UAO study. From this data, over 90% of the patients who were extubated successfully had a PRP on PS < 250 , and a PRP on CPAP < 400 . Hence, the recommendations will be to wean PS if PRP is < 250 , to maintain PS if PRP is between 250 and 400, and to increase PS if PRP is > 400 . Ultimately, the clinician will make the final determination regarding whether or not to make the wean, or to extubate the patient.

The decision to begin non-invasive ventilation after extubation will be left to the clinician. NIV management will be per clinician choice, and we will not implement a NIV protocol.

Diaphragm ultrasound measurements will occur daily, and will be conducted by two providers who will remain blinded to each-other's measurements. We will place an ultrasound probe over the right hemi-diaphragm just lateral to the nipple line between and compute Diaphragm Contractile Activity (DCA). DCA is obtained by measuring the thickness of the right hemi diaphragm and calculating the percent difference between diaphragm thickness on inspiration and exhalation. We will also use ultrasound to measure diaphragm thickness on exhalation and monitor how this changes serially over time as a measure of the architecture of the diaphragm.

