[figure not shown]

Figure 1: High Level view of Flow Diagram of Study

Study Outcomes

The following study outcomes will be followed for each of the proposed study objectives.

1. **Objective:** To refine the esophageal manometry based effort of breathing weaning protocol so that it can be used easily, and can attain high protocol adherence for eventual use in a randomized controlled trial. **Outcome:** protocol adherence for each

Effort of breathing guided ventilator management for children: a pilot study

Protocol Version Date: March 2, 2021

recommendation, as well as qualitative data on the reasons for rejection of the recommendation. This will guide refinement of the protocol.

2. **Objective:** To demonstrate that integration of these two pieces of software together can be used safely to provide recommendations for ventilator management. **Outcome:** PRP values used to generate each recommendation will be tracked, and raw data will be recorded at least twice daily to compare calculated PRP values from the software program to the post-processing program we currently use for the UAO study. Will also track reasons for rejecting recommendations (above), specifically targeting any recommendations which were rejected because of perceived problems with the software or calculations (incorrect data etc).
3. **Objective:** To determine the potential magnitude of reduction in length of mechanical ventilation afforded by using such a weaning tool, to help determine estimated sample size for a future randomized controlled trial. **Outcomes:** The primary outcome is the total length of ventilation (invasive and non-invasive). Secondary outcomes include length of invasive ventilation, length of non-invasive ventilation, re-intubation rates, use of inhaled medications to treat UAO, use of steroids for UAO, post-extubation ICU length of stay. Sedation level will be tracked as this is a potential confounding variable, as well as fluid balance, details about endotracheal tubes, use of blood pressure medications, as well as procedures.

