The endpoints of the study for individual patients will occur 48 hours after extubation. . The bands and esophageal catheter will be removed 1 hour after extubation for study purposes. However, if the clinical team would like to use the catheter or bands for ongoing patient management, it can be left in place but will no longer be considered a study specific intervention. The patient will be followed for 48 hours to track therapies and re-intubation.

7. Analysis and Sample Size

In performing sample size calculations for the eventual proposed RCT, with an anticipated 1 day reduction in effort of breathing between intervention and control groups, the expected number of patients will range from 300-700 patients per arm. For this reason, the eventual study would need several years to complete, or be performed as a multi-center RCT. Estimates of treatment effect generated from this study will help refine these estimates.

For this pilot study, the requested sample size is 40. The sample size has been increased from the initial 20 to 40 to accommodate the changes in the CDS tool platform, the protocol changes to the effort of breathing algorithm, and the diaphragm ultrasound measurements. We believe this sample size is necessary to test all of the stated objectives. By objective

1. Refining esophageal manometry protocol: It is anticipated that 40% of patients will pass the initial SBT. This means that 10-12 patients will be left to test the protocol. Each patient should generate 10-20 recommendations on the weaning protocol, giving approximately 100 recommendations to test. Based on preliminary analysis of the 20

included patients to date, and in discussions with the bedside providers, we have modified the esophageal manometry protocol to allow for 3 ranges of adjustment, rather than 2. It is believed that this will improve adherence, while still meeting the physiologic principles of titration of ventilator support to maintain effort of breathing. The subsequent 20 patients would then be used to test if the revised protocol attains high adherence.

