2. Software pieces: Each patient should receive at least 24 recommendations on the CDS portion of the protocol and for those that fail the SBT, another 10-20 recommendations on the weaning protocol. We have migrated the CDS tool out of Microsoft Access, making it available in a web-browser to improve compatibility with clinical care. The rules of the protocol have not changed. The additional analysis will be to confirm that users can follow the new user interface. This should afford enough data to test the reliability of the software. From the 10-12 patients who are enrolled in the weaning protocol, at least 2 time points will be available to compare PRP values between the software tool and the post-processing program, allowing > 20 points for direct comparison.
3. Magnitude of reduction: It is anticipated that the expected duration of MV for those with anticipated lengths > 48 hours ranges from 5-7 days on average, with a wide range. While it is unlikely that we will have a definitive answer about the magnitude of effect, approximately 20 patients should provide data to get a reliable estimate of mean and standard deviation for length of ventilation to use in future calculations.
4. TPP separation: It is anticipated that 20 patients should yield a minimum of 60 TPP measurements (average 3/patient) which can be used to identify a potential separation between PEEP recommended by the protocol, and that which would be recommended by normalizing TPP. From the preliminary data we have to date (approximately 9 patients), there appears to be an average separation of 2 cmH₂O between clinician chosen PEEP and PEEP at TPP, although the variation is large. However, most of the time clinician chosen PEEP is below the evidence based recommendations. If we can demonstrate that for at least 50% of the observations (95% Confidence Interval 40-60%) there would be a separation of at least 2 cmH₂O, it would facilitate development of a protocol. To achieve this level of confidence, we would need a minimum of 50 observations.
5. NIV protocol: It is anticipated that 40% of patients who are extubated will be placed on NIV after extubation. This means that 10-12 patients will be left to test the protocol. Each patient should generate 10-20 recommendations on the NIV weaning protocol, giving approximately 100 recommendations to test.

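### The software check compares PRP values but not the recommendation bands they produce, and its point count is a floor based on 20 patients rather than the 40 requested

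*Combined protocol and SAP*

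**What the plan says.** Objective 2 (section 3, and Study Outcomes item 2 in section 6) is to show that the two pieces of software together can safely supply recommendations for ventilator management.

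Study Outcomes item 2 gives three strands of evidence:
- The PRP behind each recommendation is tracked.
- For a reference comparison, "raw data will be recorded at least twice daily to compare calculated PRP values from the software program to the post-processing program".
- Reasons for rejection are tracked, with attention to rejections that clinicians put down to faulty software or calculations.

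Section 7 item 2 sizes this work. It starts with counts: "Each patient should receive at least 24 recommendations on the CDS portion of the protocol", plus 10-20 weaning recommendations for each patient who fails the spontaneous breathing trial (SBT). It mentions checking that users can follow the new interface, and then states "This should afford enough data to test the reliability of the software". The PRP comparison comes next: "From the 10-12 patients who are enrolled in the weaning protocol, at least 2 time points will be available to compare PRP values", "allowing > 20 points for direct comparison".

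The weaning rule is in section 6, Study Treatments: wean pressure support (PS) below a PRP of 250, "to maintain PS if PRP is between 250 and 400, and to increase PS if PRP is > 400".

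The overall size is also in section 7: "For this pilot study, the requested sample size is 40", raised from 20. Item 1 adds: "It is anticipated that 40% of patients will pass the initial SBT".

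**The concern.** In the weaning phase the software delivers one of three recommendations, fixed by where PRP lies relative to 250 and 400. Two programs can agree closely on average and still fall on opposite sides of a cut-off for the same recording. A displayed 240 against a reference 260 is a small difference in value but a different recommendation. Comparing values alone therefore leaves open the question that Objective 2 asks.

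The other strands do not close the gap. Rejections are informative only when a clinician notices a problem, and a plausible but wrong PRP near a cut-off gives no cue. The large number of recommendations from the decision-support tool has no reference standard.

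The size of the comparison is also hard to interpret. The plan names no agreement statistic, acceptance limit or target precision for PRP, and no method for several points from one patient. Ultrasound, by contrast, has numerical limits (mean bias at most 10%, precision within 20% either way). The PRP count also appears to be carried over from the 20-patient design. What is at stake is how much the future randomised trial can rely on recommendations whose error rate was not measured.

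**Working it through.** **Inputs from the documents.** 40% pass the initial SBT, so 60% enter weaning; 10-12 weaning patients; at least 2 points each; 40 patients requested, previously 20; cut-offs 250 and 400; weaning recommendations every 2 hours, 10-20 per patient.

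**1. The plan's own count.** 10 × 2 = 20 and 12 × 2 = 24, which reproduces the stated figure (exactly 20 at the lower end). The 10-12 patients match 0.60 × 20 = 12, not 0.60 × 40 = 24.

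**2. The count on 40 patients.** 24 × 2 = 48 points. Doubling the plan's 10-12 instead gives 20-24 patients and 40-48 points. The per-patient floor is roughly right: 10-20 recommendations at 2-hour intervals cover 20-40 hours, and two recordings per 24 hours give 1.7-3.3 points.

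**3. What these counts can exclude.** With zero discordant bands in n independent points, the one-sided 95% upper limit is 1 − 0.05^(1/n).

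| n | Upper limit |
|---|---|
| 20 | 13.9% |
| 24 | 11.7% |
| 40 | 7.2% |
| 48 | 6.1% |

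**4. Chance of seeing no discordance.** If 5% of points were truly discordant, the chance of observing none is 0.95^20 = 36%, 0.95^24 = 29% and 0.95^48 = 8.5%.

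**5. Clustering.** With two points per patient, effective n = n/(1 + ICC). The documents give no intraclass correlation (ICC), so the range is shown. At ICC 0, the limits are those above. At ICC 1, effective n is 10, 12 and 24 for 20, 24 and 48 points, and the limits are 25.9%, 22.1% and 11.7%.

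**6. Precision of the value comparison.** The half-width of the 95% interval for a limit of agreement, in units of the SD of the differences, is t × sqrt(1/n + 1.96²/(2(n − 1))). This gives 0.81 at n = 20, 0.73 at n = 24 and 0.50 at n = 48, before clustering.

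**7. Can small errors change the band? (Illustration on assumed inputs only.)** The documents give neither the spread of PRP nor the software's error. Suppose PRP is uniform over 100-500 and the error is unbiased with a 10% coefficient of variation (CV). Discordance is then about 0.798 × 0.10 × (250 + 400)/400 = 13.0%. With a lognormal PRP (median 200-300, log-SD 0.5) it is about 8-11%. At a 5% CV the two assumptions give about 6.5% and 4-6%. Mean bias is zero throughout, so a comparison of averages would look good.

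**The case against.** Several counter-arguments have force.

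- **The sufficiency sentence.** A reader might infer that the plan calls 20-24 points enough. The text does not say so. The sentence follows the recommendation counts (at least 20 × 24 = 480 from the decision-support tool, or 960 on 40 patients) and the interface check, and the PRP points come afterwards. Those points are also a stated minimum, not a fixed count.
- **The role of PRP.** A reader might infer that PRP matters only through its cut-offs. Section 2 says that clinicians also weigh the trend in effort of breathing, and section 6 uses effort-of-breathing guidance in judging the SBT. Comparing values is therefore legitimate and should stay. Clinicians also make the final decision on each recommendation.
- **The consequence.** A reader might infer that Objective 2 would be declared met despite about one wrong recommendation in eight. No pass rule exists, and the 12-14% is a confidence limit after zero observed discordance, not an expected error rate.
- **Prior use.** Section 2 reports the module accurate in close to 400 patients. That counts for the calculation. No statistic is given, however, and section 2 also says that no protocol recommendations were attached to the values in that study.
- **How a recommendation is formed.** It may rest on more than one reading, since section 6 refers to PRP having been in a range and the figure with the detail is not shown. The illustration in step 7 treats single readings, so its rates should not be carried over to recommendations.
- **Existing data.** Band concordance can be derived from recordings already planned. This is correct, and it makes the gap one of analysis rather than data collection.

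**Conclusion.** The point holds as a gap in the analysis plan. The only reference-based check of the software compares PRP values, while Objective 2 concerns recommendations that depend on three PRP bands. Tracking perceived faults would not reveal unnoticed band changes. The stated count is a floor on 20 patients; the same reasoning on 40 gives about 48 points. That lowers the zero-discordance upper limit from 12-14% to about 6% if points are independent, or from 22-26% to about 12% if points within a patient are fully correlated.

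These limits depend on the plan's SBT pass rate and its two points per patient. The 8-13% discordance at a 10% CV is illustrative, because both the PRP spread and the error are assumed. The documents do not support saying that the planned data are insufficient: without a criterion, sufficiency is unsupported rather than disproved.

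**What to change.** - **Keep the value comparison** and specify it: Bland-Altman bias and limits of agreement by a method that allows for repeated points per patient.
- **Add band concordance** on the same recordings: classify each program's PRP as below 250, 250-400 or above 400. Report the percentage discordant and its direction, with a patient-clustered confidence interval. If no discordance is seen, a clustered bootstrap collapses to zero width, so give the exact limit with the number of patients as the conservative denominator.
- **Use all twice-daily recordings** from weaning patients in both blocks of 20. For the first block, which preceded the three-range rule, apply the current cut-offs to the paired values.
- **Restate section 7 item 2** for 40 patients: about 24 in weaning and at least 48 points, with the discordance rate those points can exclude, before and after clustering. Replace the general sufficiency statement with that figure.

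The cost is some extra post-processing of segments already recorded, and new wording. No added patients or procedures are needed. The downside for the sponsor is a less favourable, but interpretable, statement of reliability.

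### The TPP criterion counts gaps of 2 cmH₂O without a sign or a patient effect, so on its own it cannot tell a systematic or repeatable PEEP difference from scatter

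*Combined protocol and SAP*

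**What the plan says.** Section 3, objective 4, asks how TPP-guided PEEP differs from PEEP set by a PEEP/FiO₂ table. Section 6 (Study Treatments) schedules a measurement twice a day, at the current PEEP and after PEEP is changed to bring TPP to zero. Section 6 (Study Outcomes, item 4) lists TPP on the protocol's PEEP and the PEEP needed for a TPP of zero. It states no criterion and no direction.

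The criterion is in section 7, item 4:

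- The comparison is "a potential separation between PEEP recommended by the protocol, and that which would be recommended by normalizing TPP".
- The expected yield is that "20 patients should yield a minimum of 60 TPP measurements (average 3/patient").
- The target is that "for at least 50% of the observations (95% Confidence Interval 40-60"%) the gap reaches the threshold: "there would be a separation of at least 2 cmH₂O, it would facilitate development of a protocol".
- The sample-size statement is "To achieve this level of confidence, we would need a minimum of 50 observations".
- The preliminary data, from about 9 patients, concern a different pair of settings: "there appears to be an average separation of 2 cmH₂O between clinician chosen PEEP and PEEP at TPP, although the variation is large". The next sentence adds that "most of the time clinician chosen PEEP is below the evidence based recommendations".

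Nowhere is it stated which PEEP must be the higher for an observation to count. There is no criterion for the mean difference, no SD, and no allowance for measurement repeatability or for several measurements coming from one patient.

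**The concern.** Without a sign, a gap of 2 cmH₂O or more can be read as absolute or as directed, and the same data can pass one reading and fail the other. On the absolute reading the share rises with spread alone. Three quite different states can therefore give the same result: a consistent shift in one direction, stable differences between patients that go both ways, and noise around the table value. The first two would give a TPP-based protocol something to act on; the third would not.

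At stake is how well the pilot answers objective 4. A share above 50% could be taken as evidence that the strategies separate when the data do not show whether the separation is real.

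**Working it through.** **The plan's own figure.** A 95% CI of 40–60% around 50% needs n = 1.96² × 0.5 × 0.5 / 0.10² = 96.04, so 97 observations, not the stated 50. With 50 the half-width is 1.96 × √(0.25/50) = 13.9 points (36.1–63.9%); with 60 the interval is 37.3–62.7%. This shortfall is a separate matter and the present point does not rest on it.

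**Inputs from section 7, item 4.** Threshold 2 cmH₂O; required share 50%; 60 observations from 20 patients, average 3 each. **Assumptions.** Normal scatter, and SDs from 2 to 5 cmH₂O, because no SD is given.

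**Formulas.** Let D = PEEP at TPP zero minus protocol-recommended PEEP, with mean μ and SD σ.

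- Absolute share: P(|D| ≥ 2) = 1 − Φ((2 − μ)/σ) + Φ((−2 − μ)/σ).
- Signed share: P(D ≥ 2) = 1 − Φ((2 − μ)/σ).
- For μ = 0 the absolute share is 2 × (1 − Φ(2/σ)). It equals 50% at σ = 2/0.6745 = 2.97.
- For μ = 2 the absolute share is 0.5 + Φ(−4/σ) and the signed share is 0.5.

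| SD | μ=0, absolute | μ=0, signed | μ=0, chance that at least 30 of 60 qualify (absolute) | μ=2, absolute | μ=2, signed |
|---|---|---|---|---|---|
| 2 | 31.7% | 15.9% | 0.2% | 52.3% | 50% |
| 2.5 | 42.4% | 21.2% | 14% | 55.5% | 50% |
| 3 | 50.5% | 25.2% | 58% | 59.1% | 50% |
| 4 | 61.7% | 30.9% | 98% | 65.9% | 50% |
| 5 | 68.9% | 34.5% | 99.9% | 71.2% | 50% |

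The fourth column is a binomial tail with independent observations. Clustering would widen the spread of the observed share, so those chances are a guide only. On the signed reading with μ = 0, the chance of at least 30 of 60 is below 1% at every SD in the table.

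**Same share, different states.** An absolute share of 50% arises from μ = 0 with SD 2.97, and also from μ = 2 with SD 1 (0.5 + Φ(−4) = 50.0%). Now write D as mean plus patient effect plus session effect, so that σ² = between-patient variance + within-patient variance. With μ = 0 and σ = 4 the expected share is 61.7% whether all 16 units of variance lie between patients (fully repeatable) or all lie within patients (not repeatable at all). The count does not distinguish them.

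**Sensitivity.** If PEEP is read in whole cmH₂O, an observation counts once |D| ≥ 1.5, and an SD of 1.5/0.6745 = 2.22 is enough. With heavier tails (t, 3 df) the SD needed is about 4.5.

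**Pooling.** With 3 measurements per patient the design effect is 1 + 2 × ICC. An assumed ICC of 0.2 to 0.8 gives 1.4 to 2.6, so 60 observations carry the information of 60/1.4 = 43 down to 60/2.6 = 23. A high ICC is what repeatable patient-level differences would produce, and it is also when a pooled interval is most over-precise.

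**The case against.** The strongest reply is that the undirected count is the right quantity. Objective 4 asks about a difference between two strategies, not whether one sets PEEP higher on average. TPP-guided PEEP is individualised and may move either way. If the mean difference is zero but 62% of observations differ by 2 cmH₂O or more, and those gaps are real, the strategies do separate. This stands. A reader might infer that the criterion should apply to one named direction only; the documents do not support that, and it could discard real two-way separation. What the reply does not supply is evidence that the gaps are real, and the plan asks for none.

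Two further replies also stand. Item 4 says that meeting the figure would facilitate protocol development, and Study Outcomes item 4 says without condition that the data will guide it. A reader might infer a go/no-go rule, but nowhere does the plan say that development stops below 50%. A reader might also take the preliminary average of 2 cmH₂O, and the remark "although the variation is large", as showing that the criterion sits on a knife edge or that scatter will meet it. Both describe clinician-chosen PEEP, whereas the criterion concerns protocol-recommended PEEP, and the plan itself says that these usually differ. Neither figure can be carried across.

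Finally, signed differences and repeats within patients can be recovered from the planned data. That makes the fix cheap; it does not put the analysis in the plan.

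**Conclusion.** The point holds as a limit on what the criterion can show. The plan's one numeric criterion for the TPP objective has no sign and pools repeated measurements. By itself it cannot distinguish a systematic shift or a repeatable patient-level difference from noise.

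The size depends on an SD that the documents do not give. Under zero-mean normal scatter the criterion is met in expectation from SD 2.97 upward (61.7% at SD 4). At SD 2 the expected share is 31.7%, and 30 of 60 independent observations would qualify only 0.2% of the time. The finding is therefore that scatter could meet the criterion, not that it will. The 50% signed share at a mean of 2 rests on symmetry. This is an inexpensive improvement to one objective of a pilot, not a flaw that invalidates it.

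**What to change.** In section 7, item 4:

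1. Keep the 50% share and state that it is absolute.
2. Define the signed difference as PEEP at TPP zero minus protocol-recommended PEEP.
3. Report the shares at +2 cmH₂O or more and at −2 cmH₂O or less separately.
4. Report the mean signed difference with its CI, and the between- and within-patient SDs, from a model with a patient random effect.
5. State that the 50% share supports a TPP protocol only alongside a non-zero mean difference, or between-patient differences that persist across sessions.

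Section 7, item 6 is a precedent: for ultrasound it sets separate requirements for mean bias and for precision.

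No new data are needed. The costs are slightly more analysis and a criterion that is harder to meet. One limit remains: sessions are at different times, so within-patient variation mixes measurement error with true change, and the model cannot fully separate the two.

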Schematic illustrations are displayed in Figures 1-5. After consent, an esophageal catheter will be placed. The CDS tool for ventilator management will be placed at the bedside (on a laptop computer) for each enrolled patient, and recommendations regarding changing ventilator support will be provided to the clinicians every 2 hours or with a new arterial blood gas. Clinician decisions and changes to the ventilator with respect to each recommendation will be tracked. PEEP and FiO₂ management is based on current best evidence. Twice a day, transpulmonary pressure measurement will be obtained (a. on the current PEEP/FiO₂ combination- as recommended by the current best evidence and b. PEEP will be changed to make transpulmonary pressure zero). TPP measurements are obtained through an expiratory and inspiratory hold on the ventilator while the patient is not breathing significantly spontaneously. This methodology will be identical to what is already approved as part of another ongoing investigation at CHLA (CCI-13-00370). This data will be tracked to help generate a new protocol based on TPP. PEEP will be returned to the previous level after TPP calculations are complete. Once the patient meets criteria for spontaneous breathing (see flow diagram below, Figure 1), they will enter the effort of breathing weaning arm of the study.

In this weaning arm of the study, there will first be an oxygenation test to ensure the patient can tolerate lower levels of PEEP and FiO₂ in preparation for weaning. If they fail, they will go back to the previous ventilator settings and an oxygenation test will not be repeated again for 24 hours. If they pass, they will go to a 2 hour Spontaneous breathing trial. Esophageal manometry, spirometry, and Respiratory Inductance Plethysmography (RIP) bands will be in place. If they pass based on clinical criteria as well as guidance from the esophageal manometry protocol regarding effort of breathing and other pieces of extubation failure (such as direction of the Konno Meade plot as an indication of neuromuscular weakness) the recommendation will be to extubate. If the clinician elects not to extubate, the reasons will be tracked.

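### Fifty transpulmonary pressure observations give a 95% CI of about 36–64%, not 40–60%; the stated interval needs about 97 independent observations

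*Combined protocol and SAP*

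**What the plan says.** Section 7 (Analysis and Sample Size), item 4, expects that "20 patients should yield a minimum of 60 TPP measurements (average 3/patient" on average. The quantity of interest is the share of observations in which the two ways of setting PEEP differ by at least 2 cmH₂O. The target is to show this "for at least 50% of the observations (95% Confidence Interval 40-60" per cent). The plan says that such a result "it would facilitate development of a protocol", and then gives the number required: "To achieve this level of confidence, we would need a minimum of 50 observations".

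Section 6 (Methods and Procedures), Study Treatments, describes the measurement: "Twice a day, transpulmonary pressure measurement will be obtained", and only "while the patient is not breathing significantly spontaneously". Each patient can therefore contribute several observations.

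Section 7 sets the total sample at 40, raised from 20. Item 4 is still written for 20 patients. It shows no formula and makes no allowance for repeated measurements in a patient.

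**The concern.** A proportion, a confidence level and a half-width together determine the number of independent observations. Item 4 states all four quantities, and the number is roughly half of what the other three imply. The expected yield of 60 also falls short.

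The calculation counts observations as if each came from a different patient. If a patient with a large PEEP separation at one reading tends to show one at the next, 60 readings from 20 patients carry less information than 60 independent readings.

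What is at stake is how far the estimate can be relied on. The result is meant to inform a later TPP-based ventilator protocol, and whoever takes that step would believe the proportion is known to within 10 points when it is not. The consequence stops there. No hypothesis test or stopping rule uses the figure, and section 6 has PEEP returned to its prior level after each TPP calculation.

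**Working it through.** **Inputs.** From section 7, item 4: p = 0.50; 95% CI 0.40–0.60, so half-width d = 0.10; stated minimum n = 50; expected yield 60 from 20 patients, so m = 3 per patient. From section 7: total sample 40. The documents give no intraclass correlation (ICC).

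**1. Trying to reproduce the plan's figure.** Half-width = 1.96 × √(p(1−p)/n).

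- n = 50: 1.96 × √(0.25/50) = 0.139, giving 36.1–63.9%.
- n = 60: 1.96 × √(0.25/60) = 0.127, giving 37.3–62.7%.

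Neither reaches 40–60%.

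**2. Number needed.** n = 1.96² × 0.25 / 0.10² = 96.04, so 97.

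**3. Confidence that 40–60% really carries.** z = 0.10/√(0.25/n).

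- n = 50: z = 1.414, or 84.3%.
- n = 60: z = 1.549, or 87.9%.

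**4. Whether another method explains 50.**

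| Method | n needed for 40–60% | 95% CI at n = 50 |
|---|---|---|
| Wald | 97 | 36.1–63.9% |
| Wilson | 93 (96.04 − 3.84 = 92.2) | 36.6–63.4% |
| Clopper-Pearson | 104 (smallest even n) | 35.5–64.5% |
| Wald, continuity-corrected | 106 | 35.1–64.9% |
| One-sided 95% bound | 68 (1.645² × 0.25/0.01 = 67.6) | lower bound 38.4% |

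A finite-population correction gives 96.04/(1 + 95.04/60) = 37.2 for a population of 60, or 53.6 for 120. Neither is 50, and the correction does not suit inference to future patients. Fifty observations give ±10 points only if p(1−p) = 50 × 0.01/1.96² = 0.130, that is, p near 15% or 85%.

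**5. Clustering (illustration only; every ICC is assumed).** With exactly 3 readings per patient, the design effect is 1 + 2 × ICC.

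| Assumed ICC | Design effect | Effective n of 60 | Half-width at 60 | n needed for ±10 |
|---|---|---|---|---|
| 0 | 1.0 | 60 | 12.7 | 97 |
| 0.1 | 1.2 | 50 | 13.9 | 116 |
| 0.3 | 1.6 | 37.5 | 16.0 | 154 |
| 0.5 | 2.0 | 30 | 17.9 | 193 |

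If the number per patient varies (assumed coefficient of variation 0.5), the design effect becomes 1 + (1.25 × 3 − 1) × ICC = 1 + 2.75 × ICC. The half-widths at 60 are then 14.3, 17.1 and 19.5 points for ICC 0.1, 0.3 and 0.5.

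**6. If all 40 patients contributed 3 readings each (assumed).** n = 120 gives 1.96 × √(0.25/120) = 0.089, or 41.0–59.0% under independence. The half-width exceeds 10 points once the ICC is above (120/96.04 − 1)/2 = 0.125, or above (120/96.04 − 1)/2.75 = 0.091 with the varying cluster size.

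**The case against.** The strongest reply is that the trial now enrols 40 patients. At item 4's own yield of 3 per patient, that is 120 observations and about 41–59% under independence, which is inside the target. This part stands: the study as now sized may deliver the precision wanted, and the corrected text should let the reader see that. It does not make 50 a correct minimum. Item 4 states a yield only for 20 patients, the reasons section 7 gives for enlarging the sample do not mention TPP, and the margin is lost at an ICC of about 0.12.

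A second reply is that the target is a proportion of 50% or more, and a larger proportion needs fewer observations. But the stated interval is centred on 50%, and even p = 0.70 would need 1.96² × 0.21/0.01 = 80.7, so 81.

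Third, the ICC and cluster-variation figures are not from the documents. That is true, and the arithmetic error stands without them. The illustration also uses 1.96 where 20 clusters would call for a t multiplier (19 df). That would widen the equal-cluster half-widths to about 14.8, 17.1 and 19.1 points, so the simplification favours the plan.

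Finally, this is a descriptive pilot objective, and section 7 sets out little formal analysis for any objective. That is fair, and it is why the point is minor. It does not excuse a wrong precision statement.

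**Conclusion.** The concern holds. At a proportion of 50%, a 95% CI of 40–60% needs about 97 independent observations (93 to 106 across the two-sided methods tried), not 50. Fifty give a half-width of 13.9 points and the expected 60 give 12.7, against the stated 10. These figures follow from item 4's own numbers and assume only independence, which is the favourable case. Repeated readings within patients can be expected to make the shortfall larger, but by an amount that cannot be stated without an ICC.

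Severity is minor: the error lies in the claimed precision of a pilot estimate, and no test, stopping rule or patient's management depends on it.

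**What to change.** Replace the sentence on 50 observations with wording such as: *If the true proportion is 50%, 50 independent observations give a 95% CI of about 36–64% and 60 give about 37–63%; a CI of 40–60% would need about 97 independent observations, and more if measurements within a patient are correlated.*

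Then:

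- Keep the 50% benchmark for the observed proportion. Report that proportion with a patient-clustered CI (a patient-level bootstrap, or GEE with a small-sample-corrected robust standard error), together with the observed ICC.
- Restate the expected precision for the number of patients who will actually contribute TPP data. Item 1 of section 7 mentions a preliminary analysis of the 20 "included patients to date, and in discussions with the bedside providers". If TPP was recorded in those patients, use their yield and ICC. The 120-observation case can be given as a conditional example.
- Do not promise ±10 points, and do not take 3 readings per patient as given. TPP is measured only when the patient has no significant spontaneous breathing, so the yield will vary.

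The cost is one rewritten sentence and a clustered interval on data already being collected, with no added patients. The downside is that the stated precision becomes less favourable, and an ICC estimated from about 20 patients will itself be imprecise.
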